#### 7.5.1.2 Paternal exposure

Male patients should refrain from fathering a child or donating sperm during the study and for 7 days after the last dose of topical ruxolitinib.

Pregnancy of the patient's partner is not considered to be an AE. However, the outcome of all pregnancies (spontaneous miscarriage, elective termination, ectopic pregnancy, normal birth, or congenital abnormality) occurring from the date of the first dose until 7 days after the last dose should, if possible, be followed up and documented.

## 7.6 SAFETY REPORTING CRITERIA TO THE PHARMACEUTICAL COLLABORATORS

All Serious Adverse Events ("SAE") required to be reported pursuant to the Protocol shall be provided to Incyte and its representatives by Institution or Principal Investigator within twenty-

*Abbreviated Title:* Topical ruxolitinib in cGVHD

*Version Date:* 01/25/2021

four (24) hours of learning of the event as well as any additional reports (including follow-up) agreed upon by Institution or Principal Investigator and Incyte. SAE Reports will be sent to [REDACTED]. By sending to this e-mail address, the Incyte Pharmacovigilance group will receive copies of the reports. This process will be tested and established before the first patient is enrolled in the Study. Notwithstanding anything to the contrary herein, Institution will have the primary responsibility of reporting adverse events ("AE") to regulatory authorities.

Leidos will send all reports to the manufacturer.

## **7.7 DATA AND SAFETY MONITORING PLAN**

### **7.7.1 Principal Investigator/Research Team**

The clinical research team will meet on a biweekly basis when patients are being actively treated on the trial to discuss each patient. Decisions about dose level enrollment and dose escalation if applicable will be made based on the toxicity data from prior patients.

All data will be collected in a timely manner and reviewed by the principal investigator or the medical advisory investigator. Adverse events will be reported as required above. Any safety concerns, new information that might affect either the ethical and or scientific conduct of the trial, or protocol deviations will be immediately reported to the IRB using iRIS and to the Sponsor.

The principal investigator will review adverse event and response data on each patient to ensure safety and data accuracy. The principal investigator will personally conduct or supervise the investigation and provide appropriate delegation of responsibilities to other members of the research staff.

### **7.7.2 Sponsor Monitoring Plan**

As a sponsor for clinical trials, FDA regulations require NIAMS to maintain a monitoring program. The NIAMS program allows for confirmation of: study data, specifically data that could affect the interpretation of primary study endpoints; adherence to the protocol, regulations, and SOPs; and human subject's protection. This is done through independent verification of study data with source documentation focusing on:

- Informed consent process
- Eligibility confirmation
- Drug administration and accountability
- Adverse events monitoring
- Response assessment.

This trial will be monitored by personnel employed by Leidos, a NIAMS contractor. Monitors are qualified by training and experience to monitor the progress of clinical trials. Personnel monitoring this study will not be affiliated in any way with the trial conduct.

*Abbreviated Title:* Topical ruxolitinib in cGVHD

*Version Date:* 01/25/2021

## 8 STATISTICAL CONSIDERATIONS

### 8.1 STATISTICAL HYPOTHESES

#### 8.1.1 Primary efficacy endpoints:

The primary objectives are to determine the safety and tolerability as well as the efficacy of topical ruxolitinib 1.5% cream in patients with epidermal cGVHD.

The primary safety and tolerability endpoint will be counts of the grades of adverse events noted. The primary efficacy endpoint will be the percent change in the surface area of the target lesions for ruxolitinib-treated vs. placebo-treated lesions.

#### 8.1.2 Secondary Efficacy endpoints:

The secondary endpoints are: 1) change in pain, pruritus, and overall severity VAS scales and 2) the pharmacokinetics and pharmacodynamics of topical ruxolitinib 1.5% cream in patients with epidermal cGVHD.

### 8.2 SAMPLE SIZE DETERMINATION:

The primary objectives are to determine the safety and tolerability as well as the efficacy of topical ruxolitinib 1.5% cream in patients with epidermal cGVHD. Patients who are compliant with protocol requirements through the primary endpoint, week 6, are considered evaluable. To analyze the efficacy of the treatment, we will measure surface area percent change. The initial surface area of each of the two target lesions will be measured at baseline and again at week 2, week 4 (optional), and week 6 on evaluable patients after one lesion has received treatment with ruxolitinib 1.5% cream and the other lesion has received treatment with the vehicle control. Following 6 weeks of treatment, the percent decline in the surface area of the two lesions will be determined, and the difference between the two decline percentages between the two lesions will be formed, expressed consistently as ruxolitinib decline minus placebo decline. If there are 10 evaluable patients (complete all study requirements through week 6) who have differences in decline percentages determined, then there will be 80% power to detect whether these paired differences in the changes from baseline are equal to one SD of the difference of the changes (effect size=1.0) using a two-tailed 0.05 significance level paired t-test. In practice, a Wilcoxon signed rank test may be used instead of a t-test if the differences are not consistent with a normal distribution ( $p<0.05$  by a Shapiro-Wilks test).

The anticipated accrual rate is 1 patient per month. Enrollment is open to individuals at least 12 years of age, regardless of gender or racial/ethnic background. Given the complexity of this disease, which is often multiorgan in nature with intermittent flares of disease, the drop-out rate is expected to be high. In order to allow for a modest percentage of patients who are not able to comply with the proper administration of the two agents, the accrual ceiling will be set at 15 patients. Therefore, it is anticipated that the study will last approximately 17 months to reach 10 evaluable patients.

**Abbreviated Title:** Topical ruxolitinib in cGVHD

**Version Date:** 01/25/2021

### **8.3 POPULATIONS FOR ANALYSIS**

Per protocol analysis dataset: patients who receive at least 80% of scheduled doses of the agent in order to measure the change from baseline to 6 weeks will be included in the statistical analyses performed.

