## 3.2 DRUG ADMINISTRATION

Topical ruxolitinib cream and vehicle cream will be supplied by Incyte in containers labeled with a perforated label as active study drug or placebo. The pharmacy will remove the perforated label and apply a label containing site of administration as well as label A or B according to the randomization table. Participants will be carefully instructed regarding the site of application of each cream. Neither the study drug nor the vehicle cream should be applied to areas of skin with ulceration. Participants will be provided with photographs of the body site to apply each cream as a guide at home for application. Application will be twice a day (12 hours apart) for 6 weeks.

**Abbreviated Title:** Topical ruxolitinib in cGVHD

**Version Date:** 01/25/2021

Application should occur at approximately the same time each day and at least 2 hours before showering/bathing. Participants should wear gloves when applying cream. A new pair of gloves should be used when applying cream to the second site. This will minimize the possibility of cross contamination. Medication and vehicle cream will be applied as a thin layer. Patients will be asked to complete a medication diary (APPENDIX G).

If a dose is missed, it should be applied as soon as possible on the same day unless it is within 1 hour of the next dose. If it is within 1 hour of the next dose, the missed dose should not be applied. Missed doses will not be reported to the IRB as a protocol deviation unless the patient misses > 5 doses per month.

During application of the study drug and the vehicle, care should be taken to avoid the eyes and mouth. If study drug or vehicle are ingested, study staff should be contacted immediately. If the cream is applied to the participant's body by a pregnant individual, that individual should use gloves and a wooden applicator to apply the creams on to the participant.

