### 3.3 DOSE MODIFICATIONS

**Table 1: Dose Modifications**

All dose modifications will be discussed with the PI or MAI.

Adverse event	CTCAE grade/attribution	Protocol Action
Any adverse event (excluding ulceration, infection, treatment-related malignancy)	Grade 2 >7 days that is probably or definitely related to study drug.	Hold study drug; *If AE resolves to ≤ grade 1 or baseline within 7 days: resume dose. ** If AE does not resolve to ≤ grade 1 or baseline within 7 days: patient comes off drug.
Any adverse event (excluding ulceration, infection, treatment-related malignancy)	Same grade 2 >7 days recurs that is probably or definitely related to study drug.	Hold study drug; *If AE resolves to ≤ grade 1 or baseline within 7 days: decrease dose to once daily. **If AE does not resolve to ≤ grade 1 or baseline within 7 days: patient comes off drug.
Any adverse event (excluding ulceration, infection, treatment-related malignancy)	Same grade 2 >7 days recurs after dose reduction that is probably or definitely related to study drug.	Patient comes off drug.
Any adverse event (excluding ulceration,	Grade 3 that is probably or definitely related to study drug.	Hold study drug; *If AE resolves to ≤ grade 1 or baseline within 7 days:

**Abbreviated Title:** Topical ruxolitinib in cGVHD

**Version Date:** 01/25/2021

infection, treatment-related malignancy)		decrease dose to once daily. **If AE does not resolve to $\leq$ grade 1 or baseline within 7 days: patient comes off drug.
Any adverse event (excluding ulceration, infection, treatment-related malignancy)	Same grade 3 recurs after dose reduction that is probably or definitely related to study drug.	Patient comes off drug.
Any adverse event (excluding ulceration, infection, treatment-related malignancy)	Grade 4 that is probably or definitely related to study drug.	Patient comes off drug.
Skin ulceration at treatment site	Any grade	Patient comes off drug.
Infection	Grade 2 that is probably or definitely related to study drug.	Hold study drug until completion of systemic antibiotic course and resolution of infection, then restart at same dose level.
Infection	Grade 2 recurs that is probably or definitely related to study drug.	Hold study drug until completion of systemic antibiotic course and resolution of infection, then decrease dose to once daily.
Infection	Grade 2 recurs after dose reduction that is probably or definitely related to study drug.	Patient comes off drug.

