Infection	Grade 3 that is probably or definitely related to study drug.	Patient comes off drug.
Infection	Grade 4	Patient comes off drug.
Treatment-related malignancy	Grade 3	Patient comes off drug.
Treatment-related malignancy	Grade 4	Patient comes off drug.

Exceptions to the above treatment modifications:

1. Alopecia any grade

**Abbreviated Title:** Topical ruxolitinib in cGVHD

**Version Date:** 01/25/2021

2. Dry skin any grade
3. Grade 2 skin or soft tissue infection at untreated site
4. Grade 2 paronychia

Doses withheld while recovering from an adverse event should not be made up.

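### Section 8.3 does not say whether doses held or reduced under Table 1 count as missed, so a protocol-compliant week-6 completer can be evaluable in one section and excluded from the analysis in another

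*Combined protocol and SAP*

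**What the plan says.** Section 8.3 is the only section that sets analysis populations, and it sets one. It is a per-protocol set of patients who receive "at least 80% of scheduled doses of the agent", and this set is used for the statistical analyses. No intention-to-treat, modified intention-to-treat or sensitivity set is defined for efficacy.

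Section 3.2 gives the only dosing schedule: "Application will be twice a day (12 hours apart) for 6 weeks".

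Table 1 in section 3.3 orders departures from that schedule for events judged probably or definitely related to study drug:
- First related grade 2 event lasting more than 7 days: "Hold study drug; *If AE resolves to ≤ grade 1 or baseline within 7 days: resume dose".
- Recurrence of that event, or a related grade 3 event: hold and, if it resolves within 7 days, "decrease dose to once daily".
- Related grade 2 infection: "Hold study drug until completion of systemic antibiotic course and resolution of infection, then restart at same dose level". No maximum length is given.

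The text after the table adds: "Doses withheld while recovering from an adverse event should not be made up". Section 3.1.1 also holds both creams until any event of grade 3 or higher resolves.

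Evaluability is defined elsewhere without a dose percentage. Section 8.2 says: "Patients who are compliant with protocol requirements through the primary endpoint, week 6, are considered evaluable". Section 6.3.1 asks for completion of 6 weeks of treatment and also admits earlier skin progression. The Précis (Design) asks that the participant still be active at the primary endpoint. Section 8.4.2 describes the lesion measurements and the paired test on evaluable patients and does not mention the 80% set.

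**The concern.** A patient whose cream is held or reduced as the protocol orders, and who attends week 6 with both lesions measured, has complied with the protocol. That patient counts towards the 10 evaluable patients in 8.2. If scheduled doses means the planned 84, 8.3 can still remove the same patient from the analysis.

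The trigger for removal would be an adverse event, usually one attributed to study drug, so membership of the efficacy set would depend on something that happens after treatment starts. The estimate would then describe patients who tolerated close to full dosing, in a study where tolerability is itself a primary objective. With about 10 patients, each exclusion is about a tenth of the data. Because the term is undefined and 8.3 and 8.4.2 point to different sets, the choice could also be made after the results are known.

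The point concerns week-6 completers only. New rules for patients who stop early or progress would not settle it.

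**Working it through.** **Inputs.** Twice daily for 6 weeks (3.2); 80% threshold (8.3); holds and reductions (Table 1, 3.1.1); held doses not made up (3.3); 10 evaluable patients, effect size 1.0, two-sided 0.05 paired t-test, 80% power, ceiling of 15 (8.2).

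**The plan's own figure.** Exact power of the paired t-test uses the noncentral t distribution with n − 1 degrees of freedom and noncentrality d√n. With n = 10 and d = 1.0 this gives 0.803, so the stated 80% is reproduced.

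**Doses needed.** 2 × 42 = 84 applications per site. 0.80 × 84 = 67.2, so at least 68 are needed and at most 16 (8 full days) may be missed.

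**Holds followed by a return to twice daily**, doses received = 84 − 2 × (days held):

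| Days held | Doses received | Share of 84 | Meets 80% |
|---|---|---|---|
| 7 | 70 | 83.3% | yes |
| 8 | 68 | 81.0% | yes |
| 9 (infection, length assumed) | 66 | 78.6% | no |
| 10 (infection, length assumed) | 64 | 76.2% | no |
| 14 (two 7-day holds, or one assumed 14-day infection hold) | 56 | 66.7% | no |

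A single 7-day hold leaves room for two other missed doses. A third gives 67/84 = 79.8% and fails. Section 3.2 treats up to 5 missed doses a month as not reportable as a deviation.

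**Once-daily dosing from day d to day 42**, ignoring any hold before it: 2(d − 1) + (43 − d) = d + 41. At least 68 requires d ≥ 27. Starting on day 26 gives 67, which fails.

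**Related grade 3 event: 7-day hold from day D, then once daily to day 42.** Once-daily days = 42 − D + 1 − 7 = 36 − D, so doses received = 84 − 14 − (36 − D) = D + 34. Day 15 gives 49 (58.3%), day 22 gives 56 (66.7%) and day 29 gives 63 (75.0%). The patient falls below 68 if the hold starts on day 33 or earlier.

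**Power if accrual stops at 10 evaluable under 8.2 and 8.3 then removes some**, at effect size 1.0: n = 9 gives 0.748 and n = 8 gives 0.681.

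**The case against.** The strongest reply is that 84 is only one reading of the denominator. After a reduction, a patient's schedule could be taken to be once daily, and doses that are not to be made up could be taken as no longer scheduled. On that reading the patient stays in. Section 8.4.2, with its reference to evaluable patients, points the same way. This stands as a limit: a reader might infer that the plan definitely drops these patients, and the documents do not go that far. They support an undefined term and a conflict between sections. The reply does not remove the point, because 8.3 is the only populations section and nothing in it adopts the modified schedule.

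A reader might also infer that power must fall. It need not. Section 8.2 allows 15 patients, expressly to cover those who cannot apply the two creams properly, so excluded patients can be replaced. Replacement restores the number but not the patients who were selected out.

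A reader might further infer that the effect estimate is inflated by a calculable amount. The documents give no rate of holds and no effect in patients with modified dosing. Section 11.1.2 reports mostly mild to moderate related events, which suggests that few patients would be affected. Nor can an inflation example and the power loss above be presented together. The power figures assume that the removed patients benefit as much as the others. If 8 patients average 1.0 SD and 2 have no benefit (common SD 1, by simulation), power is about 0.55 with all 10 kept and 0.68 with the two removed, so in that case exclusion does not cost power.

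Two further limits hold. Each patient carries both creams and leaves as an intact pair, so no imbalance between treatments arises; the issue is whom the estimate describes. Safety is unaffected, since 3.1.1 and 6.3.1 make all treated patients evaluable for toxicity.

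**Conclusion.** The point holds as an unresolved conflict with a concrete consequence. Against the only schedule in the documents, a patient who follows Table 1 and completes week 6 can fall below 68 of 84 applications and be excluded under 8.3, while being evaluable under the Précis, 6.3.1 and 8.2 and falling within the test as 8.4.2 describes it. That exclusion would rest on adverse events after treatment starts.

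Its reach is limited. One hold of up to 8 days with no other misses does not trigger it; a longer hold, a repeat hold, a reduction early enough, or one hold plus several missed doses does. Infection-hold lengths are assumed. How many patients would be affected cannot be estimated. The fall in power from 0.80 to 0.75 or 0.68 applies only if accrual closes at 10 under 8.2, one or two are then removed without replacement, and the effect stays at 1.0 SD in those who remain. The change is worth making because it is cheap and settles the analysis set before the data are seen.

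**What to change.** - In 8.3 and 8.4.2, run the primary paired test on every patient with baseline and week-6 areas for both lesions, regardless of protocol-directed holds or reductions.
- Keep the set with at least 80% of the planned 84 applications as a named sensitivity analysis. Define scheduled doses there, and state whether the agent means the active cream only or both creams.
- Reconcile the evaluability definitions in the Précis, 6.3.1, 8.2, 8.3 and 8.4.2, so that the count that closes accrual is the set analysed.

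The cost is wording only. The medication diary in Appendix G already records whether a dose was forgotten or held, so no new data are needed, and no dosing rule changes. The downside is that the estimate may be somewhat less favourable, and power somewhat lower, if patients on reduced dosing benefit less.

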### **8.4 STATISTICAL ANALYSES**

#### **8.4.1 General approach**

The analysis will primarily focus on evaluating the difference in the surface area of the target lesions receiving active agent or placebo in each patient and testing whether the target lesions improve more with active agent compared to placebo.

#### **8.4.2 Analysis of the primary efficacy endpoints**

To analyze the efficacy of the treatment, the initial surface area of each of the two target lesions will be measured at baseline and again at week 2, week 4 (optional), and week 6 on evaluable patients after one lesion received treatment with ruxolitinib 1.5% cream and the other lesion received treatment with the vehicle control. Following 6 weeks of treatment, the percent decline in the surface area of the two lesions will be determined, and the difference between the two decline percentages between the two lesions will be formed, expressed consistently as ruxolitinib decline minus placebo decline. The magnitude of the paired differences will be calculated and tested for whether the difference is equal to zero by a two-tailed 0.05 significance level paired t-test. In practice, a Wilcoxon signed rank test may be used instead of a t-test if the differences are not consistent with a normal distribution (p<0.05 by a Shapiro-Wilks test).

#### **8.4.3 Analysis of the secondary efficacy endpoints**

The secondary objectives will be assessed using the following measures. Measures of disease activity in patients with epidermal cGVHD will be determined. These include the pain, pruritus, and overall disease severity VAS scales.

To describe pharmacokinetics and pharmacodynamics of topical ruxolitinib 1.5% cream in patients with epidermal cGVHD, standard pharmacokinetic parameters such as AUC, clearance, concentration and half-life will be reported using descriptive statistics, along with pharmacodynamic parameters such as pSTAT3.

#### **8.4.4 Safety Analyses**

Safety of the agent will be assessed by reporting the grade of adverse events noted in each patient, and reporting the fraction with grade 3 and grade 4 adverse events. Safety data will be presented in individual listings. Summaries will also be prepared. The safety data will consist of the reporting of all adverse events, vital signs, physical examination data, and appropriate laboratory safety data.

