**Design:**

- This is a Phase II, placebo-controlled, double-blinded study to determine the safety, tolerability and efficacy of topical ruxolitinib in patients with epidermal cGVHD.
- Participants with at least 2 non-ulcerated sites of epidermal cGVHD will apply topical ruxolitinib 1.5% cream to 1 prespecified site and vehicle cream to the second prespecified site twice a day for 6 weeks.
- Safety will be assessed according to CTCAE v5.0 criteria. Assessments will occur during visits and/or phone follow-up every 2 weeks during treatment.
- Efficacy will be assessed at 6 weeks. The initial surface areas of the 2 target lesions will be measured at baseline, week 2, and week 6 on evaluable patients, with the option for an in-person assessment at week 4. The percent decline in the surface area of the 2 lesions will be determined, and the difference in decline between the 2 lesions will be calculated, expressed consistently as ruxolitinib decline minus placebo decline.
- A skin biopsy and peripheral blood samples will be collected prior to treatment and at week 6 to evaluate the cutaneous immune compartment cellular infiltrate, cytokine profiling, STAT phosphorylation, gene expression profiling, and in situ cGVHD biomarkers.
- Pharmacokinetic studies will be performed at week 2.
- Up to 15 patients will be enrolled to achieve 10 evaluable patients, defined as participants who remain active at the time of the primary endpoint. 10 evaluable patients will provide 80% power to detect whether these paired differences in the changes from baseline are equal to one SD of the difference of the changes (effect size=1.0) using a two-tailed 0.05 significance level paired t-test. In practice, a Wilcoxon signed rank test may be used instead of a t-test if the differences are not consistent with a normal distribution ( $p<0.05$  by a Shapiro-Wilks test).

**Abbreviated Title:** Topical ruxolitinib in cGVHD

**Version Date:** 01/25/2021

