### **3 STUDY IMPLEMENTATION**

#### **3.1 STUDY DESIGN**

This is a phase II, placebo controlled study to evaluate the safety, tolerability, and efficacy of 1.5% topical ruxolitinib cream, INCB018424, in patients with epidermal cGVHD. Case series and anecdotal reports of systemic JAK inhibitors in cGVHD have suggested a benefit for cGVHD involvement of the skin and other organs, warranting further study. For patients with cGVHD that manifests with primarily epidermal skin disease, effective topical therapy is desirable. Current topical therapies (corticosteroids and calcineurin inhibitors), can have significant side effects and are not specific to the disease pathology.

In this study, patients with a minimum of 2 distinct areas of involvement with intact (no ulceration) epidermal cGVHD that has been confirmed histologically, will be eligible for participation. Each participant will receive active study agent and placebo. Chronic GVHD is a heterogeneous disease with a waxing and waning course. Given the heterogeneity and the natural history of this disease as well as use of concurrent systemic medications, each participant will serve as his/her own control to allow for better comparison of placebo and active study drug. Randomization table generated by [name], statistician, will be provided to the pharmacy, such that the labeling of placebo and active study drug as container A and B will be randomized at the pharmacy. All participants will be provided with active study drug to apply to the designated affected area (maximum application BSA of 10%) twice a day and a second container containing a vehicle cream to be applied twice a day on a second affected area. Subjects who experience dose limiting toxicities (DLT) will have the dose adjusted as described in Section 3.1.1.

**Abbreviated Title:** Topical ruxolitinib in cGVHD

**Version Date:** 01/25/2021

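### Sections 8.1.1 and 8.4.4 pool application-site adverse events from both creams and specify no ruxolitinib-versus-vehicle contrast for local tolerability

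*Combined protocol and SAP*

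**What the plan says.** Safety and tolerability is one of the two primary objectives (1.1.1). Section 8.1.1 defines its endpoint: "The primary safety and tolerability endpoint will be counts of the grades of adverse events noted". It names no unit, site or cream. Section 8.4.4 reads: "Safety of the agent will be assessed by reporting the grade of adverse events noted in each patient". It adds the fraction with grade 3 and grade 4 events and takes all adverse events as its data. On presentation it says: "Safety data will be presented in individual listings. Summaries will also be prepared". The content of the summaries is not stated.

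The design could support more. Section 3.1 says that "each participant will serve as his/her own control to allow for better comparison of placebo and active study drug". Under 3.2 the pharmacy will "apply a label containing site of administration as well as label A or B according to the randomization table". The primary efficacy analysis in 8.4.2 is explicitly paired, ruxolitinib site minus placebo site.

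Event location is already used elsewhere. Table 1 in 3.3 has a row for "Skin ulceration at treatment site", and its exceptions include "Grade 2 skin or soft tissue infection at untreated site". These separate treated from untreated skin but not one cream from the other. The Appendix G diary has a site number, a location and a column for observations such as irritation. The Appendix F scales are scored per site.

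**The concern.** The point concerns application-site events only. Every patient is exposed to ruxolitinib, so for all other events the patient is the right unit and no within-patient control exists.

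For local events the design does provide a control: a vehicle site on the same patient, with the cream allocated at random. The safety analysis specifies no use of it. Followed literally, a grade 2 or higher reaction under the vehicle cream is reported as part of the agent's safety. A reader of the pooled result could not tell whether local reactions came from the drug, from the vehicle base or from both. That affects the interpretation of one half of the primary objective.

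Causality assessment does not fill the gap. The Précis says: "This is a Phase II, placebo-controlled, double-blinded study". Relatedness is therefore judged without knowing which site carries ruxolitinib. It also appears only in the dose-limiting toxicity and dose-modification rules (3.1.1, 3.3), not in 8.1.1 or 8.4.4.

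**Working it through.** **The plan's own figures.** No figure is stated for the safety endpoint. The 80% power in 8.2 concerns efficacy only. It reproduces (exact paired t-test, n = 10, effect size 1.0, two-sided 0.05: 0.803) and has no bearing here.

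**Inputs**
- Number of patients: the accrual ceiling is n = 15 (8.2). All treated patients are evaluable for toxicity (3.1.1, 6.3.1).
- Grades: grade 1 events are not collected (6.1.1), so the rates below are for grade 2 or higher.
- Per-site risk p: not given in the documents. Assumed at 2%, 5% and 10%.
- Equal risk at the two sites: an assumption. Section 11.1.2 reports similar frequencies of cutaneous events on vehicle-treated and ruxolitinib-treated lesions, but in other populations and without rates.

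**Step 1: event counts.** Count each affected site once. Expected vehicle-site events are 15p and expected events at both sites together are 30p. The vehicle share is 15p/30p = 1/2, whatever the within-patient correlation. The chance of at least one vehicle-site event is 1 - (1 - p)^15.

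| Assumed p | Expected vehicle-site events | Chance of at least one |
|---|---|---|
| 2% | 0.30 | 26% |
| 5% | 0.75 | 54% |
| 10% | 1.50 | 79% |

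**Step 2: patients affected only at the vehicle site.** Among patients with any local event, this share is (p - p11)/(2p - p11), where p11 = p² + φp(1 - p) is the chance of an event at both sites and φ is the within-patient correlation.
- φ = 0: at p = 2%, 0.0196/0.0396 = 49%; at p = 10%, 0.09/0.19 = 47%.
- φ = 0.5: at p = 2%, 0.0098/0.0298 = 33%; at p = 10%, 0.045/0.145 = 31%.
- φ = 1: 0%, because both sites always react together.

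**Step 3: the pooled figure carries no direction.** Suppose ruxolitinib has 5% risk and vehicle 10%, with independent sites. The share of patients with any local event is 1 - 0.95 × 0.90 = 14.5%, and the expected count is 15 × (0.05 + 0.10) = 2.25. Swapping the two creams gives the same two numbers.

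**Step 4: grade 3/4 fraction.** One patient with a vehicle-site-only event moves it by 1/15 = 6.7 points. Assumed risks of 1-2% per site give a 14-26% chance of at least one vehicle-site event (1 - 0.99^15 and 1 - 0.98^15). These are upper-bound illustrations. Section 11.1.2 reports one severe or life-threatening event attributed to topical ruxolitinib in over 2350 subjects. If 1/2350 = 0.04% were used as the per-site risk, the chance in 15 patients would be 1 - (1 - 1/2350)^15 = 0.6%. That figure comes from other diseases and from drug-attributed events, so it is not a vehicle-site rate in cGVHD either.

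**Step 5: could the contrast be tested?** The exact McNemar p-value with k discordant patients all in one direction is 2 × 0.5^k: 0.0625 for k = 5 and 0.031 for k = 6. At least six one-way discordant patients out of 15 would be needed, so only a descriptive table is realistic.

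**The case against.** The strongest reply is that this is silence, not error. Section 8.4.4 promises individual listings of all adverse events. With at most 15 patients, a listing that carries location could be split by hand after unblinding. The CRFs are not among the documents, so nobody can say that a site field is missing. This stands in part: a contrast may still be obtainable. But the plan does not commit to one, and site is best recorded when the event occurs.

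Second, counting vehicle-site events is conservative, because it can only raise the agent's count. This stands in full. A reader might infer that pooling understates or hides harm from ruxolitinib; the documents do not support that. Nor is a vehicle-site event certainly free of ruxolitinib: 3.2 recognises possible cross-contamination, although 1.2.3 describes systemic absorption as minimal.

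Third, the per-site pain and pruritus scales already give local symptom data. They do, but 8.1.2 and 8.4.3 class them as secondary efficacy and disease activity, with no between-site contrast stated. Whether to read them as tolerability as well is a matter of judgement and not part of this point.

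Fourth, the numbers rest on assumptions and the table may be nearly empty. This also stands. Rates well above 10% per site for grade 2 or higher would have no support in the documents: 11.1.2 describes the common possibly related events as mild to moderate.

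**Conclusion.** The point holds as a gap in specification. Sections 8.1.1 and 8.4.4 pool local events from both creams and specify no ruxolitinib-versus-vehicle contrast for local tolerability, although cream is randomised by site within each patient. The loss is one of interpretation: local events cannot be assigned to a cream from the specified result.

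Under the equal-risk assumption, half of the expected local events belong to the vehicle site. With 2-10% risk per site in 15 patients, that is 0.3-1.5 events of grade 2 or higher and a 26-79% chance of at least one. Patients affected only at the vehicle site would be 31-49% of those with any local event for correlations from 0 to 0.5, falling to none under full concordance. Grade 3/4 local events are probably much rarer.

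Two stronger readings fail. One is that the trial cannot produce the contrast: the listings might allow it. The other is that all adverse events should be split by cream: only local events can be. No sample size, test or stopping rule depends on the contrast, so this is a cheap improvement rather than a threat to the trial.

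**What to change.** In 8.1.1 and 8.4.4, state that:
- each adverse event is recorded as at site 1, at site 2 or at neither, if the CRF does not already do so;
- after unblinding, application-site events are tabulated by maximum grade for ruxolitinib sites and vehicle sites, with the paired counts of patients (ruxolitinib only, vehicle only, both, neither), labelled descriptive and without a test;
- all other adverse events are reported per patient.

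The cost is one extra table and possibly one CRF field. Visits, patient numbers, the efficacy analysis, sample size and alpha are unchanged. The downside is low precision: with at most 15 patients and no grade 1 events collected, the table is likely to be sparse and should be presented as such.
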